The proposed study tests the novel DilaCheck® device *in vivo*. The target population is women presenting to the hospital for evaluation of labor or admitted to the Labor and Delivery unit for management of the first stage of labor. The Sponsor (Elm Tree Medical Inc.) trains providers working on the Labor and Delivery unit in the use of DilaCheck®. After informed consent, each patient participant is randomized to receive either two cervical dilation examinations with standard methods or two cervical dilation examinations using the device. Two practitioners complete the cervical examinations separately. The primary outcome is inter-examiner agreement between the control and device arms. Secondary outcomes include agreement of subjective measurements with DilaCheck® measurements over time, agreement of providers' device readings with a blinded reviewer's, patient and provider satisfaction, and documentation of adverse events. Planned enrollment is 50 participants over one year. We hypothesize that the device will increase agreement between the two practitioners from about 49% to 90%, as demonstrated in the simulator trial. The long-term objective is to validate DilaCheck® for use in increasing precision in cervical dilation measurements so that this tool may be available to Labor and Delivery providers to enhance quality of care for pregnant mothers. Increased precision in cervical dilation measurements will enable providers

to make better recommendations for admission to the hospital, augmentation or induction of labor, and cesarean section.

The proposed study is a randomized, controlled trial comparing inter-examiner agreement of standard methods for measuring cervical dilation to a novel medical device. The research population is pregnant women in the first stage of labor.

TRIAL PROTOCOL

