The second provider will enter the hospital room. The second provider will introduce him/herself to the patient and explain that s/he is going to perform a cervical examination. The trial coordinator will record the time of the second exam. The second exam must be completed within 10 minutes of the first exam. The second provider will complete a cervical examination following standard techniques. The provider will write his/her measurement of cervical dilation on a second Data Collection Form, fold the form, and hand it to the trial coordinator. Readings may be integers or fractional answers. The second provider will leave the room.

If the patient is in the Device Group: The first provider will introduce him/herself and inform the patient that s/he is going to conduct a cervical examination and confirm that the patient is ready to proceed. The trial coordinator will record the time of the first exam. The first provider will complete a cervical examination with a DilaCheck® device and sterile gloves using the techniques taught during training.

During or after the examination, before looking at the DilaCheck® device or his/her hand, the provider will verbally report his/her subjective cervical dilation measurement to the trial coordinator. Readings may be integers or fractional answers. The trial coordinator will record this number. The first provider will then look at the DilaCheck® device and read the measurement from the DilaCheck® measuring tape.

The trial coordinator will take a photograph from a secure camera of the DilaCheck® measurement. The trial coordinator may choose to take multiple photographs to ensure a clear image is captured. The coordinator and provider will use a neutral background to ensure no private health information (such as an image of the patient participant or hospital room) is included in the photograph. A white sheet of paper with the subject number will be provided to serve as a blank, secure background for the photograph(s).

The first provider will record two readings of the DilaCheck® measurement. The provider will write his/her measurements on the first Data Collection Form, fold the form, and hand it to the trial coordinator. The first will be his or her reading of the exact DilaCheck® measurement, which may be a fraction (any fraction). The second reading will be his or her reading of the DilaCheck® measurement rounded to the nearest integer; i.e. the second response can only be an integer, not a fraction.

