Photograph Review. The Sponsor will train an independent reviewer to read DilaCheck® measurements. The reviewer will be provided the photographs taken of DilaCheck® measurements. The reviewer will report two measurements for each photograph. The first will be his/her reading of the exact DilaCheck® measurement, which may be a fraction. The second reading will be his/her reading of the DilaCheck® measurement rounded to the nearest integer; i.e. the second response can only be an integer, not a fraction.

Continuous Feedback. After any individual provider completes five examinations with DilaCheck®, the provider will be provided feedback about whether his/her DilaCheck® measurement readings match those of the independent reviewer.

Power Calculation. The planned enrollment in the study is 50 patients. The following assumptions were used for the power calculations. The agreement in the Control Group was projected to be 49%,⁴ and the agreement in the Device Group was projected to be 90%, based on the results of the simulator trial. The standard deviation was projected to be 23, also based on the standard deviation in the prior simulator trial. With a two-tailed test with $\alpha=0.05$, a sample size of five yields 80% power. However, a trial with five participants will not yield the desired robustness in evaluation of a novel medical device. Instead, a sample size of 25 subjects in each group is planned to allow for examinations across a wide range of patients and providers. A sample size of 50 yields a power of 100% to detect a difference between the two methods given the above assumptions.

Statistical Analysis. The statistical analysis will use a two-tailed level of significance of 0.05. Using SPSS, the proportion of examinations in each group for which the two providers' examinations differed will be determined. A Students T test will be performed to determine whether this difference is significant. The number of examinations for which providers' answers differed by one centimeter and by two or more centimeters for each group will be determined. A Students T test will be performed to determine if the frequency of variation of one centimeter significantly differed between groups. A Students T test will be performed to determine if the frequency of variation of two or more centimeters significantly differed between groups. These analyses will be completed for both the fractional and integral (non-fractional) sets of DilaCheck® measurement readings.

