For participants in the DilaCheck® arm, the subjective and DilaCheck®

DilaCheck® Trial

measurements will be plotted along an X-Y axis and the Pearson correlation coefficient between the two data sets will be calculated. This analysis will be completed for both the fractional and integral (non-fractional) sets of DilaCheck® measurement readings.

The photographs of the DilaCheck® measurements will be read by an independent, blinded reviewer to report the DilaCheck® measurements. The provider's and reviewer's DilaCheck® measurements will be plotted along an X-Y axis and the Pearson correlation coefficient between the two data sets will be calculated. This analysis will be completed for the fractional and integral (non-fractional) sets of DilaCheck® measurement readings.

The correlation between the providers' subjective and DilaCheck® measurements will be analyzed over time. To do so, for providers who complete at least 10 exams, the correlation of the two measurements in the provider's first half of examinations will be compared to the providers' second half of measurements. A T-test will be completed to determine whether the two correlations differ significantly. The analysis will be repeated for both the fractional and integral (non-fractional) sets of DilaCheck® measurement readings and using the data sets of readings from the independent reviewer.

The average pain score in each group will be calculated, and a Students T test will be performed to determine whether pain scores differed significantly between groups. Using logistic regression whether provider number, patient age, gestational age, weight, or epidural status significantly impacted likelihood of agreement or pain score within each group will be determined. The average provider confidence in accuracy will be calculated, and a Students T test will compare if patients' confidence differs significantly between groups. Logistic regression will be used to determine if provider experience or training significantly predicted likelihood of agreement.

Any additional statistical analysis appropriate for the data collected will be performed. For the qualitative data, including descriptions of adverse events and feedback, each of the responses will be reviewed individually. Any serious adverse events will be reported. Any informative feedback or themes in the feedback will also be collated.

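### The over-time analysis keeps only providers with at least 10 exams, but only 50 exams carry paired readings, so at most five providers can qualify and the share of data used depends on an unplanned provider number

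*Combined protocol and SAP*

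**What the plan says.** The Protocol Summary lists the outcome: "Secondary outcomes include agreement of subjective measurements with DilaCheck® measurements over time". The Statistical Analysis section restricts the analysis to those "for providers who complete at least 10 exams". It compares the subjective-device correlation in the first half of a provider's exams with that in the second half by a t-test, and repeats this for fractional and integer readings and with the independent reviewer's readings.

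Each patient is "randomized to receive either two cervical dilation examinations with standard methods or two cervical dilation examinations using the device" (Protocol Summary). The subjective estimate that pairs with a device reading is taken only in the Device Group, where, "before looking at the DilaCheck® device or his/her hand, the provider will verbally report his/her subjective cervical dilation measurement" (Data Collection).

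On size, the Power Calculation section states that "a sample size of 25 subjects in each group is planned to allow for examinations across a wide range of patients and providers". No number of providers is planned. The only figure is the Benchmarks target of training at least two, and participation is voluntary (Provider Enrollment). Under Continuous Feedback, "After any individual provider completes five examinations with DilaCheck", that provider is told whether his or her tape readings match the reviewer's.

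**The concern.** A 10-exam entry rule is demanding when only 50 exams can count. Every extra provider who examines a device patient lowers the average number of exams per provider, yet the sample size was justified partly by wanting many providers. Depending on how many take part and how they share the work, the rule could keep nearly all of the paired readings, a small part of them, or none. The plan neither controls this nor says what happens if few or no providers reach 10. At stake is whether a stated secondary outcome can be reported and, if it can, whether it describes the participating clinicians or only one or two high-volume ones. The primary comparison is not affected.

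**Working it through.** **The plan's own figure.** The documents give no sample size or power for this analysis. The power calculation concerns the primary outcome only and does not bear on this point. It reproduces under the normal approximation, reading five as per group: 2 x (1.96 + 0.84)² x 23²/41² = 4.9, rounded up to 5.

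**Ceiling.**
- Inputs: "The planned enrollment in the study is 50 patients" and 25 per group (Power Calculation); "Two practitioners complete the cervical examinations separately" (Protocol Summary), so two exams per patient.
- Paired readings: 25 x 2 = 50.
- Qualifying providers: at most 50/10 = 5, reached only if exactly five providers do 10 device exams each.
- The rule says exams, not device exams. Counting all 50 x 2 = 100 exams would let up to ten providers pass, but only their device exams carry both readings. The ceiling therefore rests on the only workable reading.

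**How many qualify.** The provider number K is not in the documents, so a range is shown. Assumption: each of the 25 device patients is examined by two different providers drawn at random from K, with equal chances (simulated).

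| K | Mean number qualifying | Chance that none qualifies | Device exams kept |
|---|---|---|---|
| 2 | 2.0 | 0% | 100% |
| 3 | 3.0 | 0% | 99.9% |
| 4 | 3.5 | 0% | 92% |
| 5 | 2.9 | 0% | 67% |
| 6 | 1.8 | 1.6% | 41% |
| 8 | 0.57 | 50% | 12% |
| 10 | 0.18 | 83% | 4% |

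Check at K = 10: one provider's device exams follow a binomial with 25 trials and probability 2/10. The chance of 10 or more is 1.7%, and 10 x 0.017 = 0.17 expected to qualify, in line with the simulation.

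**Uneven sharing among ten providers** (weights assumed):

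| Weights | Mean number qualifying | Chance that none qualifies | Device exams kept |
|---|---|---|---|
| Two at double weight | 0.6 | 49% | 12% |
| Linear, 1 to 10 | 0.9 | 30% | 20% |
| Two at triple weight | 1.2 | 13% | 28% |
| 1/rank | 1.4 | 0.4% | 39% |

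**Precision for those who qualify.** The wording allows two readings.
- *One correlation per provider and half.* At the threshold each half has 5 pairs. For an observed r = 0.8, Fisher z = 1.099 and SE = 1/√(5 − 3) = 0.707. The limits are 1.099 ± 1.96 x 0.707, which back-transform to −0.28 and 0.99. To compare two such correlations, SE = √(2/2) = 1. For 0.5 against 0.9 the z difference is 0.92 and power is about 15%; for 0.7 against 0.9 it is 0.61 and power is about 9%. With five providers at 10 exams each, a paired t-test on r has about 32% and 13% power for the same contrasts (simulated).
- *One pooled correlation per half.* With five evenly sharing providers, 0.67 x 50/2 gives about 17 pairs per half. For r = 0.8, SE = 1/√14 = 0.267 and the interval is about 0.52 to 0.92, treating pairs as independent.

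**Feedback.** It follows the fifth device exam for every provider, so a before/after indicator is fully determined by exam number. Over exams 1 to 10 the two correlate 0.87, a variance inflation of 1/(1 − 0.87²), about 4.1. With ten evenly sharing providers, only about 8 of the 50 exams are expected to come after a provider's fifth.

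**The case against.** The best defence is that a small provider group makes the rule workable. The documents name no provider number beyond a minimum of two; with two to four providers sharing evenly, 92% to 100% of the pairs are kept, and with up to six someone almost surely qualifies. Uneven workloads are plausible too, because providers volunteer, sessions are scheduled and providers may opt out of a busy shift. Uneven sharing makes it likelier that someone reaches 10. All of this stands.

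A reader might therefore go too far in inferring that probably no provider will qualify, or that the trial cannot answer this objective. The first needs both about ten providers and roughly even sharing, neither of which is in the documents. The second ignores the small-group cases. It also overlooks that the overall subjective-device correlation in the device arm is a separate planned analysis with no threshold. Nor should the interval of −0.28 to 0.99 be quoted as the plan's precision, since it applies only if correlations are computed per provider.

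The feedback concerns tape reading, not the subjective estimate, and the planned repeat with the reviewer's readings removes direct changes in tape reading from that version. This too is a fair answer to any claim that feedback invalidates the comparison.

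The defence does not supply a planned provider number, a quota or a fallback. The general allowance for further appropriate analyses leaves an all-data model open, but does not specify it before the data are seen. A small provider group would also sit poorly with the stated reason for 25 per group.

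**Conclusion.** The concern holds in a limited form. The ceiling of five qualifying providers follows from the plan's own numbers, given that exams must mean device exams for this analysis. The loss is conditional. Under even sharing it runs from almost nothing with two or three providers, to about a third of the pairs with five, to 88% with eight and 96% with ten. With ten providers and the uneven workloads tried, 61% to 88% is lost and the result rests on about one clinician. These percentages depend on assumed provider numbers and workloads; the ceiling and the missing provider number, quota and fallback do not. This is a secondary outcome, and the change is worth making because it is cheap and removes dependence on something the plan leaves uncontrolled.

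**What to change.** In the Statistical Analysis section, drop the 10-exam threshold and the half split. Number each provider's device exams in order; Provider Number and exam time are already part of the trial procedures. Model the absolute subjective-minus-device difference on exam number with a provider effect, using all 50 pairs, and keep the repeat with the reviewer's readings that is already planned. State that any trend combines growing experience with the feedback given after five exams. Do not add a before/after-feedback term as a way of separating the two, because they could be told apart only through an assumed trend shape.

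The cost is a rewritten paragraph, with no new patients or data. There are three downsides. The measure changes from correlation to absolute difference, although that is closer to the agreement named in the Protocol Summary. A common slope across providers is assumed. And precision stays limited if most providers do only a few exams.

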Eligibility. Subjects eligible for inclusion in the study must be: pregnant women who are admitted to a Labor and Delivery unit for management or induction of labor in the first stage of labor, are able to give informed consent, are 18 years of age or greater, English-speaking, have intact membranes, and have a gestational age greater than or equal to 37 weeks (i.e. term pregnancy). Inclusion criteria also include having a functioning epidural in place or having provided consent prior to the start of labor. Exclusion criteria include progression to the second stage of labor (i.e. known dilation of ten centimeters), non-English speaking, known prior rupture of membranes, any condition that renders labor unsafe for the patient (e.g. cardiac conditions, pulmonary hypertension) and any other condition that necessitates an emergent or urgent cesarean section (e.g. non-reassuring fetal status, placental abruption, hemorrhage, cord prolapse). Patients are only consented if they have adequate pain control, either because they are not yet in labor (i.e. are admitted for an induction of labor) or have a functioning epidural. All participants are necessarily female due to the subject matter. Given the vulnerability of pregnant patients under the age of 18, this study will exclude children. There are no restrictions on eligibility based on race or ethnicity. Patients can withdraw from participation at any point in the study. DilaCheck® is FDA-cleared for use by qualified healthcare professionals for women in pregnancy and labor without any further restrictions.

Provider Enrollment. The Sponsor, TJU Principle Investigator, or trial coordinator will discuss participation in the trial with providers at the TJU Labor and Delivery unit. Providers will be given the option of participating on a volunteer basis.

Provider Training. The Sponsor will train participating providers in the use of the device. The Sponsor will use a detailed script to ensure standardization of the training. The Sponsor will use a wooden cervical simulator box to train providers to use the study device without patient involvement. The standardized training will test competency with the device using the cervical simulator. The providers will also have access to a training video to reinforce the in-person training.

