The first provider will dispose of the gloves and device. The first provider will then leave the hospital room. S/he will not speak to the second provider.

The second provider will enter the hospital room. The second provider will introduce him/herself to the patient and explain that s/he is going to perform a cervical examination. The trial coordinator will record the time of the second exam. The second exam must be completed within 10 minutes of the first exam. The second provider will complete a cervical examination as above using a DilaCheck® device. The second provider and trial coordinator will repeat the same steps as described above for the first provider. The second provider will leave the room.

Patient Survey. The trial coordinator will then ask the patient to answer the questions on the Patient Survey. The survey will elicit relevant biological and demographic variables including age, race, ethnicity, gestational age, weight, and use of epidural anesthesia. It will assess the patient's discomfort with the examinations, confidence in the accuracy of the measurements, and satisfaction with the examinations. Patients will be asked to report any side effects they experienced and to provide any comments they have.

Patient Reimbursement. The trial coordinator will offer the patient a \$25 gift certificate to thank her for participating. The patient will sign a receipt to confirm that she received the gift certificate.

Provider Survey. At the end of the trial, the trial coordinator will ask all participating providers to complete the Provider Survey. The survey will elicit the provider's years of experience, role on Labor and Delivery, opinions about inter-examiner agreement using standard methods and using DilaCheck®, and ease of use and satisfaction with the device. The survey will ask whether providers experienced any adverse events and if their patients experienced any adverse events during the trial. They will have the option to provide comments.

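### The between-arm pain test leaves out epidural status, which is already collected; it is valid but gives up precision, and a null result would not show equal comfort

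*Combined protocol and SAP*

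**What the plan says.** The Statistical Analysis section specifies the arm comparison for pain in one sentence: "The average pain score in each group will be calculated, and a Students T test will be performed". It names no covariate or stratum. The next sentence plans logistic regression of several factors, epidural status among them, on agreement or pain score, but separately within each group. The general rule is "The statistical analysis will use a two-tailed level of significance of 0.05".

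Four other places bear on the point:

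- **Eligibility:** "Patients are only consented if they have adequate pain control". There are two routes: not yet being in labor (admitted for induction) or having a functioning epidural.
- **Patient Survey:** the variables collected include "gestational age, weight, and use of epidural anesthesia".
- **Discomfort** (Protection of Human Subjects): most laboring women are said to receive an epidural and so to be unlikely to find examinations painful.
- **Randomization:** allocation is computer generated, and no stratification by epidural is mentioned.

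The plan gives no pain power calculation, no equivalence or non-inferiority margin, and no rule for reading a non-significant pain result.

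**The concern.** The protocol identifies a likely strong predictor of examination pain, admits women both with and without it, and collects it. It then omits that predictor from the one analysis that compares pain between device and control. Variation between the two kinds of women stays in the error term and widens the interval for the device effect.

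The within-arm regressions do not repair this. They show whether epidural use goes with pain inside one arm. They neither adjust the device-versus-control difference nor test whether that difference depends on epidural status. Logistic regression also needs a two-level outcome, and no cut-point for the pain score is given.

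At stake is how much the trial can say about discomfort, which the protocol lists among the risks of taking part. An imprecise comparison is easily read as reassurance when it only fails to reach significance.

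**Working it through.** **1. The plan's own figures.** No figure is given for pain. The Power Calculation section concerns agreement, projected at 49% and 90%: "The standard deviation was projected to be 23". The normal-approximation formula gives 2 × [(1.960 + 0.842) × 23 / 41]² = 4.94, so 5 per arm with 80.5% power. At 25 per arm power is 99.999%. The stated 80% and 100% are therefore reproduced if five means five per group. That SD belongs to another outcome and says nothing about pain.

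**2. Sensitivity of the pain t-test with no mixing.** The plan says "a sample size of 25 subjects in each group is planned", with two-sided alpha 0.05.

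- Detectable difference at 80% power: (1.960 + 0.842) × √(2/25) = 0.79 SD by normal approximation; 0.81 SD by noncentral t.
- Power: 18% at 0.3 SD, 41% at 0.5 SD, 79% at 0.8 SD.
- Half-width of the 95% CI: t(0.975, 48 df) × √(2/25) = 0.57 SD.

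**3. Precision given up by not adjusting.** Let s be the epidural share, d the mean pain reduction with an epidural, and 2 the SD within each stratum. The device effect is taken to be the same in both strata. All of these are assumptions. The unadjusted variance is 4 + s(1−s)d². Adjustment brings it to 4.

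| s | d | Unadjusted variance | Share removed |
|---|---|---|---|
| 0.9 | 1 | 4.09 | 0.09/4.09 = 2% |
| 0.5 | 1 | 4.25 | 0.25/4.25 = 6% |
| 0.9 | 2 | 4.36 | 0.36/4.36 = 8% |
| 0.3 | 2 | 4.84 | 0.84/4.84 = 17% |
| 0.5 | 4 | 8.00 | 4.00/8.00 = 50% |

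As effective sample size, the extremes are 50 × 4.09/4 = 51 and 50 × 8/4 = 100. At the low end the gain is negligible.

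**4. Power by simulation** (4,000 runs per setting, 25 per arm; mean pain 1 to 2 SD higher without an epidural; SD 1 in women without one).

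| Assumed device effect | Epidural share | Unadjusted t-test | Adjusted for epidural |
|---|---|---|---|
| 0.8 SD in both strata (epidural SD 1) | 25-75% | 50-73% | 77-79% |
| 0.8 SD without epidural only (epidural SD 0.5) | 25% | 32-48% | 63% |
| same | 50% | 15-26% | 38-40% |
| same | 75% | 8-11% | 16% |

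With no device effect, the unadjusted test rejected in about 5% of runs in every setting.

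Adjustment therefore restores nearly all the power of a homogeneous sample when the effect is common to both strata. It helps, but leaves power low, when the effect exists only in women without an epidural.

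**The case against.** The strongest reply is that nothing here is an error. In a randomized trial an unadjusted two-sample test is legitimate. Pain is not among the secondary outcomes named in the Protocol Summary. The plan also leaves room for any further appropriate analysis. Much of this stands: the point concerns an available improvement on a non-primary outcome. The open-ended clause is not a prespecified adjusted comparison, however, and the within-arm regressions do not supply one.

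The size can also be disputed. Both eligibility routes require adequate pain control, so women without an epidural are, at consent, women not yet in labor, and the pain gap may be small. Epidural use may be near universal. A floor effect would make the SD smaller in women with an epidural. These objections are fair, and they are why the range in the working extends down to 2%.

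A reader might infer three stronger things that the documents do not support:

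- **That chance imbalance in epidural use makes the test unreliable.** Such imbalance is already part of the test's sampling error, and type I error stays at about 5%.
- **That the plan will report a null result as equal comfort.** It says nothing of the kind. The risk lies in the absence of any margin or reading rule.
- **That mixing the two kinds of women is the main reason for low sensitivity.** With 25 per arm, even a homogeneous sample needs about 0.8 SD for 80% power.

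**Conclusion.** The point holds as a modest, nearly free gain in precision. The planned pain comparison is valid but ignores a covariate that the protocol collects and itself expects to matter. Under the assumed inputs (within-stratum SD 2, epidural share 30-90%, pain 1-4 points lower with an epidural, common device effect), adjustment removes between about 2% and 50% of the variance. The documents supply none of these inputs, so no single value can be defended.

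Separately, and whatever the adjustment, a non-significant pain result could not support equal comfort: no margin is prespecified and the 95% CI would extend about 0.57 SD either side. If the device causes discomfort only in women without an epidural, the adjusted main effect will still often miss it, with 38-40% power at a 50% epidural share and 16% at 75%. The importance is low because pain is not the primary outcome.

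**What to change.** In the Statistical Analysis section:

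1. Compare pain between arms with a linear model containing arm and epidural status at the time of the examinations. Report the adjusted difference with its 95% CI.
2. Report mean pain by arm within each epidural group, labelled descriptive. Make no claim specific to one group unless an arm-by-epidural interaction supports it. With half the women in each group there would be only about 12 per arm, so selective reading is a real hazard.
3. State that a non-significant difference is not evidence of equal comfort, because no margin is prespecified and 25 per arm has 80% power only for about 0.8 SD.

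The cost is SAP wording and one degree of freedom. The survey already asks about epidural use; the form need only make clear that the answer refers to the time of the examinations. Recruitment, procedures and clinical care do not change.
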